#### **6.6.1      Resource utilization**

Not Applicable

#### **6.6.2      Health-related Quality of Life**

Not Applicable

#### **6.6.3      Pharmacokinetics**

Not Applicable

#### **6.6.4      Pharmacogenetics/pharmacogenomics**

Not Applicable

#### **6.6.5      Other biomarkers**

Not Applicable

## **7      Safety monitoring**

### **7.1.1      Serious Adverse Events**

A Serious Adverse Event (SAE) is defined as an event which:

- is fatal or life-threatening
- results in persistent or significant disability/incapacity
- constitutes a congenital anomaly/birth defect
- requires inpatient hospitalization or prolongation of existing hospitalization, unless hospitalization is for:

- routine treatment or monitoring of the studied indication, not associated with any deterioration in condition
- elective or pre-planned treatment for a pre-existing condition that is unrelated to the indication under study and has not worsened since the start of study drug
- treatment on an emergency outpatient basis for an event not fulfilling any of the definitions of a SAE given above and not resulting in hospital admission
- social reasons and respite care in the absence of any deterioration in the patient's general condition
- is medically significant, i.e., defined as an event that jeopardizes the patient or may require medical or surgical intervention to prevent one of the outcomes listed above

Unlike routine safety assessments, SAEs are monitored continuously and have special reporting requirements; see Section

To ensure patient safety, every SAE, regardless of suspected causality, occurring after the patient has provided informed consent and until 30 days after the patient has stopped study participation must be reported to Novartis within 24 hours of learning of its occurrence.

Any SAEs experienced after this 4-week period should only be reported to Novartis if the investigator suspects a causal relationship to the study drug.

Recurrent episodes, complications, or progression of the initial SAE must be reported as follow-up to the original episode, regardless of when the event occurs. This report must be submitted within 24 hours of the investigator receiving the follow-up information. An SAE that is considered completely unrelated to a previously reported one should be reported separately as a new event.

Information about all SAEs is collected and recorded on the Serious Adverse Event Report Form. The investigator must assess the relationship to study drug, complete the SAE Report Form in English, and send the completed, signed form by fax within 24 hours to the local Novartis Novartis Drug Safety and Epidemiology Department. The telephone and telefax number of the contact persons in the local department of Novartis Integrated Medical Safety are listed in the investigator folder provided to each site and is also listed below. The original copy of the SAE Report Form and the fax confirmation sheet must be kept with the case report form documentation at the study site.

Follow-up information is sent to the same person to whom the original SAE Report Form was sent, using a new SAE Report Form stating that this is a follow-up to the previously reported SAE and giving the date of the original report. The follow-up information should describe whether the event has resolved or continues, if and how it was treated, and whether the patient continued or withdrew from study participation.

If the SAE is not previously documented in the Investigator's Brochure or Package Insert (new occurrence) and is thought to be related to the Novartis study drug, a Novartis Drug Safety and Epidemiology Department associate may urgently require further information from the investigator for Health Authority reporting. Novartis may need to issue an Investigator

Notification (IN) to inform all investigators involved in any study with the same drug that this SAE has been reported.

#### **7.1.2 SAE Reporting to Ministry of Health and Ethical Committee**

Local Novartis Turkey Drug Safety Department will report all SAEs to Ministry of Health within 7 days of receipt by Novartis. SAEs are also reported to relevant Ethics Committee simultaneously in the same frame.

Suspected Unexpected Serious Adverse Events will be collected and reported to Ministry of Health and to relevant Ethics Committee every 6 months as a line listing.

Annual Safety Report will be submitted to Ministry of Health and to relevant Ethics Committee on an annual basis.

#### **7.1.3 Pregnancies**

To ensure patient safety, each pregnancy in a patient on study drug must be reported to Novartis within 24 hours of learning of its occurrence. The pregnancy should be followed up to determine outcome, including spontaneous or voluntary termination, details of the birth, and the presence or absence of any birth defects, congenital abnormalities, or maternal and/or newborn complications.

Pregnancy should be recorded on a Clinical Trial Pregnancy Form and reported by the investigator to the local Novartis Drug Safety and Epidemiology Department. Pregnancy follow-up should be recorded on the same form and should include an assessment of the possible relationship to the Novartis study drug of any pregnancy outcome. Any SAE experienced during pregnancy must be reported on the SAE Report Form.

## **8 Data review and database management**

### **8.1 Site monitoring**

Before study initiation, at a site initiation visit or at an investigator's meeting, a Novartis representative will review the protocol and CRFs with the investigators and their staff. During the study, the field monitor will visit the site regularly to check the completeness of patient records, the accuracy of entries on the CRFs, the adherence to the protocol and to Good Clinical Practice, the progress of enrollment, and to ensure that study treatment is being

stored, dispensed, and accounted for according to specifications. Key study personnel must be available to assist the field monitor during these visits.

The investigator must maintain source documents for each patient in the study, consisting of case and visit notes (hospital or clinic medical records) containing demographic and medical information, laboratory data, electrocardiograms, and the results of any other tests or assessments. All information on CRFs must be traceable to these source documents in the patient's file. *[Data not requiring a separate written record will be defined before study start and will be recorded directly on the CRFs.]* The investigator must also keep the original informed consent form signed by the patient (a signed copy is given to the patient).

The investigator must give the monitor access to all relevant source documents to confirm their consistency with the CRF entries. Novartis monitoring standards require full verification for the presence of informed consent, adherence to the inclusion/exclusion criteria, documentation of SAEs, and of data that will be used for all primary variables. Additional checks of the consistency of the source data with the CRFs are performed according to the study-specific monitoring plan. No information in source documents about the identity of the patients will be disclosed.

## 8.2 Data collection

Designated investigator staff must enter the information required by the protocol onto the Novartis CRFs that are printed on 3-part, non-carbon-required paper. Field monitors will review the CRFs for completeness and accuracy and instruct site personnel to make any required corrections or additions. The CRFs are forwarded to the Medical Documents Reception Center of Novartis *[or CRO working on behalf of Novartis]* by field monitors or by the investigational site, with one copy being retained at the investigational site. Once the CRFs are received by Novartis *[or CRO working on behalf of Novartis]*, their receipt is recorded, the original copy is placed in Central Files, and the non-carbon-required copy is forwarded to the responsible Data Management staff for processing.

## 8.3 Database management and quality control

Data from the CRFs are entered into the study database by Novartis Data Management staff using single data entry. Verification is performed manually by a separate member of the Data Management staff by comparing the Case Report Form to the data entered into the database.

Data from the CRFs are entered into the study database by Contract Research Organization (CRO) staff following their own internal standard operating procedures that have been reviewed and approved by Novartis.

Subsequently, the entered data are systematically checked by Data Management staff, using error messages printed from validation programs and database listings. Other errors or omissions are entered on Data Query Forms, which are returned to the investigational site for resolution. The signed original and resolved Data Query Forms are kept with the CRFs at the investigator site, and a copy is sent to Novartis so the resolutions can be entered into the database. Quality control audits of all key safety and efficacy data in the database are made prior to locking the database.

Adverse events will be coded using the Medical dictionary for regulatory activities (MedDRA) terminology.

Laboratory samples will be processed centrally and the results will be sent electronically to Novartis (or a designated CRO).

## **8.4 Data Monitoring Committee**

Not required.

## **8.5 Adjudication Committee**

Not required.

# **9 Data analysis**

## **9.1 Analysis sets**

Data analysis will be performed after all of the data is collected from the enrolled patients. All MS patients and control group will be accepted as the analysis sets.

## **9.2 Patient demographics and other baseline characteristics**

Data collected for patient demographics and the baseline characteristics will be summarized by descriptive statistics with summary tables.

## **9.3 Treatments (study drug, rescue medication, other concomitant therapies, compliance)**

Data collected for treatments will be summarized by descriptive statistics with summary tables.

## **9.4 Analysis of the primary variable(s)**

Serum IL-4, IL-6, IL-8, IL-9, IL-10, IL-13, IL-17, IL-23, IFN- $\gamma$ , TNF- $\alpha$ , VLA4, CCL2, CCL5, CXCR3, CXCL13 levels, PBMC intracellular IL-4, IL-6, IL-9, IL-10, IL-13, IL-17, IFN- $\gamma$ , TNF- $\alpha$  levels, EDSS, PASAT, 9-Hole peg test, timed 25-foot walk, SDMT scores and relapse rates will be analyzed.

## **9.5 Statistical model, hypothesis, and method of analysis**

There is no special hypothesis planned for this study.

## **9.6 Supportive analyses**

Not Applicable

## **9.7 Safety variables .**

Adverse and serious adverse events and pregnancies will be summarized.

## **9.8 Sample size calculation**

Due to the lack of previous studies using all of the cytokines and chemokines and multitudinous analyses, it is difficult to estimate a precise sample size for our study. Despite this, our previous publications indicate that the basal IL-17 concentration is normally distributed with a mean of 32 pg/ml ( $\pm$ stdev of 15 pg/ml) in RRMS patients. If the true difference in the mean concentration of matched pairs is 7 pg/ml, we will need to study 50 pairs of subjects to be able to reject the null hypothesis with a power of 90%. The Type I error probability associated with this test of this null hypothesis is 0,05.

With assumption of drop out rate of 20% minimum 60 RRMS patients and 60 healthy control subjects should enroll to the study. Due to expected high rate of screen failure patients, we decided to screen 80 RRMS patients in order to reach 60 eligible RRMS subjects for the study.

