## **2 Study objectives**

### **2.1 Primary and key secondary objectives**

Primary objective of this study is:

-To evaluate the differences between serum cytokine and chemokine levels of healthy controls and multiple sclerosis patients

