### **Inclusion Criteria for Healthy Control Group**

3. Healthy people who don't have MS and aged >18.
4. Written informed consent must be obtained before any assessment is performed.

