**Table 6-2 Assessment schedule for Healthy Control Group**

Visit	1	2	3
Day	0	90±7	180±14
Obtain Informed Consent	X		
Evaluation of Inclusion/Exclusion Criteria	X		
Collecting Serum and Blood Samples	X		

Patients should be seen for all visits on the designated day with an allowed “visit window” of “7” days at visit 2 and “14” days at visit 3 , or as close to it as possible, or as shortly after it as possible, or as shortly before it as possible, etc.

At a minimum, patients will be contacted for safety evaluations during the 30 days following the last study visit or following the last administration of study treatment if there are post-treatment follow-up visits (whichever is later), including a final contact at the 30-day point. Documentation of attempts to contact the patient should be recorded in the source documentation.

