5.1. SAMPLE SIZE CALCULATION

Due to the lack of previous studies using all of the cytokines and chemokines and multitudinous analyses, it is difficult to estimate a precise sample size for our study. Despite this, our previous publications indicate that the basal IL-17 concentration is normally distributed with a mean of 32 pg/ml (\pm stdev of 15 pg/ml) in RRMS patients. If the true difference in the mean concentration of matched pairs is 7 pg/ml, we will need to study 50 pairs of subjects to be able to reject the null hypothesis with a power of 90%. The Type I error probability associated with this test of this null hypothesis is 0,05.

With assumption of drop out rate of 20% minimum 60 RRMS patients and 60 healthy control subjects should enroll to the study. Due to expected high rate of screen failure patients, we decided to screen 80 RRMS patients in order to reach 60 eligible RRMS subjects for the study.

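### The only power statement (90% from 50 matched pairs) does not apply to the primary comparison of unmatched controls and patients; at 60 per group power for 7 pg/ml is 92% to 58% for control SD 5 to 20

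*Protocol*

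**What the plan says.** Protocol 9.8 bases the sample size on IL-17 alone. It states that "our previous publications indicate that the basal IL-17 concentration is normally distributed with a mean of 32 pg/ml", with an SD of 15 pg/ml in RRMS patients, and then: "If the true difference in the mean concentration of matched pairs is 7 pg/ml, we will need to study 50 pairs of subjects", for 90% power at a Type I error of 0.05. After an allowance for 20% drop-out, "minimum 60 RRMS patients and 60 healthy control subjects should enroll to the study". SAP 5.1 repeats the paragraph, including "we will need to study 50 pairs of subjects to be able to reject the null hypothesis with a power of 90" per cent. Neither document contains another power statement.

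The comparison this should support is the primary objective in Protocol 2.1 (repeated in SAP 3.1): "To evaluate the differences between serum cytokine and chemokine levels of healthy controls and multiple sclerosis patients".

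On how controls enter the study and are analysed:

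- The control criteria in Protocol 4.1 are "Healthy people who don't have MS and aged >18" plus consent. The synopsis version refers to autoimmune disease instead of MS. Neither names a matching variable.
- Table 6-2 gives controls one visit with consent, eligibility and sampling.
- Protocol 9.1: "All MS patients and control group will be accepted as the analysis sets". No matched set is defined.
- SAP 6.5.1 lists control group versus Visit 1 among the comparisons. It assigns Mann-Whitney or the independent-sample t test to independent variables, and Wilcoxon or the paired t test to dependent ones.

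**The concern.** A paired calculation is valid when each pair supplies one difference and the SD entered is the SD of those differences. Here the two members of a supposed pair are a patient and an unrelated healthy person. No pairing is planned and the analysis will not use any. The variance that matters is then the sum of the two groups' variances, and the SD of a difference between one patient and one control is sqrt(15² + control SD²). That equals 15 only if controls do not vary at all.

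The stated power governs how a null result is read. A non-significant control-versus-patient difference in IL-17 would be judged against a stated 10% chance of missing 7 pg/ml. If controls vary as much as patients, that chance is about 28% at 60 per group.

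**Working it through.** **Inputs from the documents.** Difference 7 pg/ml, SD 15 pg/ml in RRMS patients, alpha 0.05, target power 90%, 60 patients and 60 controls (Protocol 9.8, SAP 5.1). Protocol 4 and SAP 5 instead say 80 patients are included.

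**Assumptions.** The test is two-sided, which the text does not say. The control SD is not given, so it is varied over 5, 10, 15 and 20 pg/ml.

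**Step 1: reproduce the plan's figure.** Paired formula, with 15 entered as the SD of differences:

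n = (15 × (1.960 + 1.282) / 7)² = 48.2, so 49 pairs by the normal approximation. With the t distribution, power at 50 pairs is 89.9% and 51 pairs just exceed 90%. The stated 50 pairs is therefore reproduced. A one-sided test needs only 40 to 41 pairs and does not fit.

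This works only if 15 is the SD of the within-pair difference. With equal SDs of 15 in both members, the SD of a difference is 15 × sqrt(2(1 − ρ)), which equals 15 only when ρ = 0.5. Unmatched subjects have ρ = 0, giving 21.2. With ρ = 0, power at 50 pairs is 65% by the normal approximation.

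**Step 2: power for the primary comparison.** For two independent groups, SE = sqrt(15²/n₁ + control SD²/n₂), and power comes from the noncentral t with Welch degrees of freedom. Worked case, 60 per group and control SD 15:

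SE = sqrt(225/60 + 225/60) = 2.739; 7 / 2.739 = 2.556; power 71.7% (72.4% by the normal approximation).

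| Patients / controls | Control SD 5 | 10 | 15 | 20 |
|---|---|---|---|---|
| 60 / 60 | 92% | 85% | 72% | 58% |
| 80 / 60 | 97% | 91% | 77% | 62% |
| 50 / 50 | 87% | 77% | 64% | 50% |

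The first two rows fit the primary comparison best, because it uses the baseline sample and later drop-out does not remove that sample.

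**Step 3: when is 90% reached?** The control SD must be no more than about 7.0 at 60/60 or about 10.4 at 80/60. At 50/50 no value reaches it: the limit as the control SD goes to zero is 89.9%, which is the paired figure of Step 1.

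**Step 4: what equal SDs would require.** With control SD 15, 90% power for 7 pg/ml needs 98 per group (97 by the normal approximation). The difference detectable with 90% power is 9.0 pg/ml at 60/60 and 8.4 pg/ml at 80/60.

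**Step 5: Mann-Whitney.** Under the normality that Protocol 9.8 assumes, simulated power at control SD 10, 15 and 20 is about 83%, 70% and 56% at 60/60, and 88%, 75% and 62% at 80/60.

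**The case against.** **The pairs could be visits within a patient.** The protocol's purpose section puts the before-and-after measurements first, its design rationale calls patients their own controls, and the SAP plans paired tests of Visit 1 against Visits 2 and 3. A paired calculation is the right type there: if 15 were the SD of change, 60 patients would give 94%. But the sizing text speaks of pairs of subjects and turns them directly into equal numbers of patients and controls. Controls give one sample each and play no part in within-patient contrasts. On this reading the primary comparison would have no power statement at all, and the SD of change would still be undocumented.

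**The shortfall depends on an unknown control SD.** This stands as a limit on the size. Power is at or above 90% if controls are much less variable than patients. For example, if controls shared the patients' coefficient of variation (15/32) and had a mean of 25, their SD would be 11.7 and power would be 81% at 60/60 or 87% at 80/60. The mismatch itself does not depend on the control SD.

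**Skewed data could help Mann-Whitney.** SAP 6.5.1 says non-normal distributions were seen. In a lognormal simulation with means 32 and 25 and SD 15 in both groups, Mann-Whitney power is about 88% at 60/60 and 92% at 80/60. So the normal-theory figures should be labelled as such. They follow the sizing section's own assumption.

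**The consequence is limited.** Protocol 9.5 plans no special hypothesis, 9.8 admits that a precise size is hard to give, and IL-17 is one of 15 serum analytes. That is fair, but 9.8 still quotes 90% power and derives enrolment from it.

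**Conclusion.** The concern holds. The arithmetic for 50 pairs is sound, but it answers a different question: it is a paired calculation, using a between-patient SD as the SD of differences, attached to a comparison of unmatched groups. The 90% claim is unsupported for the primary objective.

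Under normality and a two-sided 0.05 test, power for 7 pg/ml at 60/60 is 72% if the control SD equals the patients' 15, with a range of 92% to 58% for control SD 5 to 20. The corresponding chances of missing the difference are about 8%, 15%, 28% and 42% at control SD 5, 10, 15 and 20, against the stated 10%. With 80 patients the equal-SD figure is 77%. The 72% is one scenario, not an estimate, because the control SD is not in the documents. The point should be fixed; it affects the stated rationale and the reading of a null result, not the conduct of the study.

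**What to change.** Rewrite Protocol 9.8 and SAP 5.1 as a two-independent-sample statement and remove the references to matched pairs and pairs of subjects. Suggested text:

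*Control versus Visit 1, independent groups, two-sided 0.05, patient SD 15 pg/ml, control SD assumed to be 15 pg/ml: 60 per group gives about 72% power for 7 pg/ml (about 70% by Mann-Whitney under normality) and 90% power for 9.0 pg/ml. If the control SD is 5, 10 or 20 pg/ml, power for 7 pg/ml is about 92%, 85% or 58%.*

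Replace the assumed control SD with an observed one if the sponsor's earlier IL-17 data provide it. Quote power at the number of patients actually planned: Protocol 4 says 80 are included, while 9.8 says 80 are screened to reach 60. If the within-patient visit comparisons are also meant to be powered, give them a separate paired statement with its own SD of change.

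The cost is wording in two sections, with no added enrolment and no change of primary objective. The stated power becomes conditional and, unless the control SD is about 7 or less at 60/60, falls below 90%.

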Patients who discontinue study drug should not be considered withdrawn from the study, unless one of the conditions listed above have been met. The sponsor should be notified about any decision regarding discontinuation of the study medication. Patients who discontinue the study drug should be treated according to the best standard of care. In addition to scheduled visits, patients who discontinue study drug due to adverse events or abnormalities on safety monitoring tests must be followed up with additional visits as needed in order to confirm the resolution of abnormalities. A Study Drug Discontinuation CRF should be completed, giving the date and primary reason for stopping the study drug.

For patients who are lost to follow-up (i.e. those patients whose status is unclear because they fail to appear for study visits without stating an intention to withdraw), the investigator should show "due diligence" by documenting in the source documents steps taken to contact the patient, e.g. dates of telephone calls, registered letters, etc.

Patients who are prematurely withdrawn from the study will be replaced by an equal number of newly enrolled patients.

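### The 20% drop-out allowance is computed as 50 × 1.2 = 60, but 60 enrolled less 20% leaves 48 patients, two short of the plan's 50 for the on-treatment contrasts; the control allowance and the replacement rule are not reconciled with it

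*Protocol*

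**What the plan says.** Protocol 9.8 and SAP 5.1 carry the same two paragraphs. The starting point is IL-17 in RRMS patients, with "stdev of 15 pg/ml". The target is set by "If the true difference in the mean concentration of matched pairs is 7 pg/ml", and from this "we will need to study 50 pairs of subjects to be able to reject the null hypothesis with a power of 90" per cent. On the error rate: "The Type I error probability associated with this test of this null hypothesis is 0,05". Neither document says whether the test is one- or two-sided.

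The drop-out step follows: "With assumption of drop out rate of 20% minimum 60 RRMS patients and 60 healthy control subjects should enroll to the study". No inflation formula is shown. On recruitment, the same section says "we decided to screen 80 RRMS patients in order to reach 60 eligible RRMS subjects for the study".

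Three other places bear on this step:

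- **Controls.** Protocol Table 6-2 lists "Collecting Serum and Blood Samples" for the healthy group at Day 0 only. Nothing is scheduled for them at Visits 2 or 3.
- **Replacement.** Protocol 5.4.9: "Patients who are prematurely withdrawn from the study will be replaced by an equal number of newly enrolled patients". The sample size sections do not mention this rule.
- **Number of patients.** Protocol 3.1 and 4, and SAP 4 and 5, speak of 80 RRMS patients recruited or included, whereas the sample size sections treat 80 as the number screened.

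**The concern.** A drop-out rate is a fraction of those enrolled, so the evaluable target should be divided by one minus the rate. The plan's 60 appears instead to come from multiplying the target by one plus the rate, which always gives too few. The stated minimum therefore does not yield the 50 evaluable pairs named in the same section.

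Two inconsistencies sit beside the arithmetic. Controls receive the same 20% although they have no follow-up from which to drop out. Patient drop-out is met by two separate devices, inflation and one-for-one replacement, without a statement of which one governs. A reader of the final report could not tell how many evaluable patients the trial was meant to have at Month 6.

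**Working it through.** **Inputs.** From Protocol 9.8 and SAP 5.1: difference 7 pg/ml, SD 15 pg/ml, alpha 0.05, power 90%, 50 pairs, drop-out 20%, minimum 60 per group. Two assumptions are needed: a two-sided test, and 15 pg/ml as the SD of the paired difference. The documents give 15 as the SD of the basal level.

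**1. Reproduce the 50.** Normal approximation for a paired test:

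n = [15 × (1.960 + 1.282) / 7]² = 48.2, so 49.

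The noncentral t gives 51, with 89.9% power at 50. The stated 50 lies between the two and is accepted. A one-sided test would give 40 (normal) or 41 (t), which does not match, so two-sided is the natural reading.

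**2. Reproduce the 60.** 50 × (1 + 0.20) = 60, which matches. 50 / (1 − 0.20) = 62.5, rounded up to 63, does not.

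**3. What 60 delivers.** 60 × (1 − 0.20) = 48, two below 50. The largest loss that still leaves 50 is (60 − 50)/60 = 16.7%.

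**4. Effect on power (paired, two-sided 0.05, difference 7, SD of difference 15).**

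| Evaluable pairs | Paired t | Normal approximation |
|---|---|---|
| 48 | 88.6% | 89.9% |
| 50 | 89.9% | 91.0% |
| 60 | 94.5% | 95.1% |

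The cost of the slip is 89.9 − 88.6 = 1.3 points by the t calculation.

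**5. Which comparisons it reaches.** SAP 6.5.1 and 6.5.2 plan four.

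| Comparison | Loss after baseline matters? |
|---|---|
| Control vs Visit 1 | No: both groups are sampled at Day 0 |
| Visit 1 vs Visit 2 | Yes: 48 pairs if the full 20% is lost by then |
| Visit 1 vs Visit 3 | Yes: 48 pairs |
| Control vs Visit 3 | Yes for patients (48); no for controls |

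The documents do not say when the 20% is lost, so 48 is the lower figure for Visit 2. The powers in step 4 apply to the two within-patient rows only. The SAP tests both control comparisons as independent groups, and neither document describes a matching procedure.

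**6. Alternative enrolment readings.** If withdrawals are fully replaced, completers stay at the enrolled number. If 80 are enrolled rather than screened, 80 × 0.80 = 64 remain.

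**The case against.** The strongest reply is that nothing material is lost. The gap is two pairs and 1.3 points of power. By normal approximation 48 pairs still give 89.9%, and by the t calculation even the plan's own 50 falls just short of 90%. The section itself warns that a precise sample size is hard to give. Sixty is a stated minimum, replacement would restore completers, and other sections put the number of patients at 80, which leaves 64.

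Most of this stands, and it limits the consequence. A reader might infer from the arithmetic that the trial fails to deliver 50 pairs and 90% power. The documents do not support that as a general statement, because the 48 arises only if exactly 60 are enrolled and withdrawals are not replaced. A reader might also infer that the comparison of patients with controls at baseline is weakened. It is not, since drop-out after Day 0 removes no baseline sample. Nor do the documents show that drop-out has definitely been provided for twice: they state an allowance and a replacement rule and leave the relation between them open.

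The reply does not rescue the sentence as written. Twenty per cent of 60 is 12, and 60 − 12 = 48. If replacement is the intended protection, the 20% allowance is unnecessary and the paragraph still needs correction. The conflict over 80 patients is a further reason to rewrite it. For controls, an allowance could cover unusable samples, but the plan does not say so.

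**Conclusion.** The drop-out inflation is wrong in both documents: 60 should be 63 for a 20% loss, or the rate should read 16.7%. The shortfall is two patients at the stated minimum. It is confined to the within-patient contrasts and the patient side of Control versus Visit 3, and it vanishes under one-for-one replacement. The power effect is about 1.3 points (88.6% against 89.9%), conditional on a two-sided 0.05 paired t-test with 15 pg/ml as the SD of the difference. This is a correction to a stated figure, not a reason to enrol more patients.

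The 20% for controls has no stated basis, given their single visit. The relation between allowance and replacement, and between 80 screened and 80 included, is unresolved.

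It would be a mistake to carry the paired power over to the control comparisons. With independent groups and SD 15, a difference of 7 needs about 97 per group for 90% power, and 60 against 60 gives about 72%. That is a separate and larger matter than the drop-out step, and correcting the inflation does not address it.

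**What to change.** In Protocol 9.8 and SAP 5.1, without changing enrolment:

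1. Replace the drop-out sentence by one of two statements: *60 enrolled patients allow for 16.7% drop-out*; or *60 enrolled patients with 20% drop-out leave 48 evaluable for the Visit 1 versus Visit 2 and Visit 3 contrasts, about 89% power for a two-sided 0.05 paired test with an SD of the difference of 15 pg/ml*.
2. Remove the drop-out allowance for controls, or state what other loss, such as unusable samples, it covers.
3. Say whether patient drop-out is handled by the allowance or by the replacement rule in Protocol 5.4.9, and state the resulting number of completers.
4. Reconcile 80 screened to reach 60 eligible with the sections that say 80 are recruited or included (Protocol 3.1 and 4; SAP 4 and 5).
5. Do not attach the paired power figure to Control versus Visit 1 or Control versus Visit 3.

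The cost is one paragraph in each document, plus consistent patient numbers in the sections named under item 4. Design and analysis are unchanged; the stated figure becomes slightly less favourable.
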